10 ADVERSE EVENTS AND TOXICITY MANAGEMENT

10.1 Safety parameters

Safety parameters will include adverse events, vital signs, RA disease severity and clinical laboratory tests.

10.2 Adverse events

An adverse event or adverse experience (AE) is any untoward medical occurrence in a subject or clinical investigation subject administered an investigational product (whether it is the experimental product or the control) and which does not necessarily have a causal relationship with the Investigational Product. An AE can therefore be any unfavourable and unintended sign, symptom, or disease temporally associated with the use of a medicinal product, whether or not considered related to the medicinal product. Pre-existing events, which increase in frequency or severity or change in nature during or as a consequence of use of a drug in human clinical trials, will also be considered as adverse experiences. AEs may also include pre- or post-treatment complications that occur as a result of protocol-mandated procedures (e.g. invasive procedures such as biopsies).

Any AE (i.e. a new event or an exacerbation of a pre-existing condition) with an onset date after IMP administration up to the last day on study (including the follow-up, off study medication period of the study), should be recorded as an AE on the appropriate CRF page(s).

An AE **does not** include:

- Medical or surgical procedures (e.g. surgery, endoscopy, tooth extraction, transfusion); the condition that leads to the procedure is an adverse event;
- Pre-existing diseases or conditions present or detected prior to start of study product administration, that do not worsen;
- Situations where an untoward medical occurrence has not occurred (e.g. hospitalisation for elective surgery, social and/or convenience admissions);
- Overdose of either study product or concomitant medication without any signs or symptoms unless the subject is hospitalised for observation.

10.2.1 Assessment of AEs

All AEs will be assessed by the Investigator and recorded on the appropriate CRF page, including the date of onset and resolution, severity, relationship to study product, outcome and action taken with study medication. See Appendix 1 for details of the NCI CTCAEv4.03 toxicity grading scale.

In addition, injection site reactions will be graded by an Investigator or designee, according to severity. It is anticipated that the subjects may find it difficult to differentiate pain and tenderness and for this reason pain and tenderness have been combined in the following grading scale:

Table 7 – Grading for Pain and Tenderness at injection sites

Mild Grade 1	Moderate Grade 2	Severe Grade 3
Awareness of symptoms but easily tolerated	Discomfort enough to cause interference with usual activities	inability to do work or usual activities

For all other reported adverse events, severity should be recorded and graded as:

Grade	Severity	Comments
1	Mild	Aware of sign or symptom, but easily tolerated. Concomitant medication is not ordinarily indicated for relief of mild AEs
2	Moderate	Discomfort enough to cause interference with usual activities. Concomitant medication may be indicated for relief of moderate AEs
3	Severe	Incapacitating with inability to work or perform usual activities. Concomitant medication may be indicated for relief of severe AEs

The relationship to study drug should be assessed using the following definitions:

Causality	Comment
Unrelated	AE is clearly due to extraneous causes (e.g. underlying disease, environment, known effect of another drug)
Unlikely	The temporal association between the AE and study drug is such that study drug is not likely to have any reasonable association with the AE
Possible	The AE could have been produced by the subject's clinical state or study drug
Probable	The AE follows a reasonable temporal sequence from the time of study drug administration, abates upon discontinuation of the study drug and cannot be reasonably explained by the known characteristics of the subject's clinical state
Definite	The AE follows a reasonable temporal sequence from the time of study drug administration, abates upon discontinuation of the study drug and/or reappears when study drug is re-introduced

These criteria in addition to good clinical judgment should be used as a guide for determining the causal assessment. If it is felt that the event is not related to study product, then an alternative explanation should be provided.

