--------------------------	--

CONFIDENTIAL

	
If the result of the serum pregnancy test is positive, the participant will be withdrawn from the study and a Pregnancy Notification Form completed. Blood samples will be collected and shipped to nominated laboratories for preparation of serum, plasma and peripheral blood mononuclear cells (PBMCs) for use in immunological analyses.
 
Subjects will be withdrawn from the study if deemed necessary by the PI if their condition cannot be sufficiently controlled with minor adjustments in treatment. All adjustments in treatment will be recorded.

Contraindications:	Severe local or systemic reactions that preclude further administration.
Safety parameters:	Refer to Table 1
Clinical procedures / assessments:	Refer to Table 1
Specialised analyses:	T-cell responses against RA autoantigens (e.g., MHC II tetramer analyses, tetramer-stimulated analyses for intra-cellular cytokines, ELISpot analyses)
Sample size determination:	No formal sample size calculation is proposed for this clinical trial. This clinical trial is a proof-of-principle study and results from this clinical trial will be utilised for power calculations for subsequent studies.
Statistical analyses:	
Planned analyses: A statistical analysis plan (SAP) will be generated prior to database lock that describes the planned statistical analysis of the study. All data will be provided in data listings sorted by treatment group, time since baseline, and subject number. Categorical data will be summarised by the number and percent of subjects falling in each category. Continuous variables will be summarised by descriptive statistics including mean, standard deviation, median and minimum and maximum. Comparisons will be made between post-treatment and pre-treatment values in the DEN181-treated group and between DEN181-treated and placebo-treated groups. Relationships between DAS28CRPv4 and descriptive data will be determined in univariate and multivariate analyses. Multilinear regression models will assess longitudinal trends.
 
Safety will be assessed by summarising adverse events and clinical laboratory tests. Adverse events will be listed and summarised by system organ class and preferred terms (current version of MedDRA) per treatment group. Vital signs and clinical laboratory tests will be tabulated and summarised per treatment group. Adverse event severity will be graded according to NIH CTCAE Version 4.03.

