4.2 Endpoints

4.2.1 Primary endpoints:

- Clinical safety observations including changes in vital signs, adverse events, serious adverse events, laboratory abnormalities and withdrawals from study. Adverse event severity will be graded according to CTCAE, Version 4.03. Any exacerbation of RA will be evaluated by using the DAS28CRPv4 scoring system.

4.2.2 Secondary endpoints:

- Proportion, total number and phenotype of naïve, effector and regulatory T-cells measured by flow cytometry and MHC II tetramer analysis pre- and post-administration of DEN-181;
- Mean changes in DAS28CRPv4 from baseline in treatment and control groups;
- Determination of the concentration of calcitriol in plasma.

4.2.3 Exploratory endpoints:

Various exploratory immune assays. These measures may include, but are not limited to measures of humoral and T-cell responses such as the following:

- Proportion and phenotype of naïve, effector and regulatory T-cells specific to other autoantigens (e.g., responses to other autoantigens including cit-vimentin);
- T-cell responses as determined by interferon-gamma (IFN- γ) enzyme linked immunospot (ELISPOT) assays to common infectious antigens (CMV, EBV, influenza);
- CD4 T-cell responses as measured by intracellular cytokine staining (ICS) (e.g., IL-2 and IFN- γ);
- Antibody titres of RA autoantigens including collagen, modified collagen and ACPA;
- Ex-vivo re-stimulation assays (e.g., as measured by cytokine secretion or tetramer analysis);
- T-cell receptor type as measured by sequence analysis on specific single cell sorted cellular populations.

Biomarker readouts may include, but are not limited to the following:

- cytokine levels;
- tryptophan/kynurenine levels (HPLC);
- metabolomics in urine;
- transcriptome analysis;
- microbiome analysis.

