10.5 Clinical Laboratory Abnormalities and Other Abnormal Assessments as AEs or SAEs

All laboratory values must be reviewed in real time by the Investigator. Given that all laboratory data are collected and statistically analysed according to their respective toxicity gradings, laboratory abnormalities that occur without related clinical symptoms and signs should generally not be recorded as AEs unless they represent a clinically significant event. Where possible, the overall diagnosis rather than the laboratory abnormality should be recorded on the AE CRF. This will avoid duplication of laboratory abnormalities in both the AE and laboratory reports. Abnormal laboratory results that are of clinical significance should be reviewed by the Medical Monitor.

Any laboratory test result that meets the criteria for a SAE (refer to Section 10.3) should be recorded as an AE, the AE page of the CRF completed and a SAE form also completed in order for the sponsor to collect additional information about that abnormality, including information regarding relationship to study product or other causes, any action taken and resolution.

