10.6 Toxicity Management

AEs and abnormal laboratory values, if appropriate, should be graded according to the NCI CTCAE v4.03 grading scale (Appendix 1). Where parameters are not addressed within the TGS, laboratory abnormalities should be assessed as “Clinically Significant” or “Not Clinically Significant”. All abnormal values should be confirmed by repeat testing as soon as possible, preferably within 3 calendar days of receipt of results prior to dose interruption or discontinuation, unless such a delay is not consistent with good medical practice.

For the purpose of monitoring toxicities, the baseline value is defined as the last value prior to the administration of the first dose of study product. This value must be obtained from the local laboratory. All management is based on changes from this value.

All results that are classified as “Clinically Significant” should be documented in the AE form of the CRF.

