10.7 Guidance for dose modification or discontinuation of treatment

To date, no specific toxicities have been identified that result from DEN-181 treatment. Any toxicities and/or abnormal laboratory findings should be investigated for aetiology and graded according to Appendix 1.

The following toxicity management will be followed:

- Grade 1 or 2: Patients may continue study treatment/placebo (except if they have an elevated temperature of >38 degrees Celsius or inter-current systemic illness). Dosing may be delayed for up to 7 days. Any dosing delays of >7 days may require that the subject is withdrawn after discussion with the Medical Monitor. Safety assessments will occur immediately prior to each dosing of IMP;
- Grade 3: Patients with any Grade 3 toxicity considered to be at least possibly related to treatment (i.e. treatment related events) should be evaluated carefully by the Investigator prior to continuing IMP treatment. Investigators may discuss individual cases with the Medical Monitor;
- Grade 4: Patients developing any Grade 4 toxicity should have treatment interrupted. The Investigator should contact the Medical Monitor to discuss the subject’s withdrawal.

Subjects will be withdrawn from treatment permanently should any of the following occur:

- Treatment related Grade 4 toxicity
- The need to take medication which could interfere with study measurements
- Subject unwilling to proceed and/or consent is withdrawn.

Where possible subjects who are withdrawn from treatment will remain on the study and attend the scheduled study visits, provided the Investigator deems it appropriate and the Sponsor approves.

Dosing will be stopped if suspected adverse drug reactions, changes to vital signs or clinical laboratory results are observed and these changes pose a significant health risk.

A corresponding adverse event will be captured within the CRF.

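### Section 10.2.1 has nearly all adverse events recorded on a three-level severity scale, while the primary endpoint and Sections 10.6 and 10.7 use CTCAE v4.03

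*Protocol*

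**What the plan says.** CTCAE v4.03 is named as the severity scale in these places:

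- Section 4.2.1 (primary endpoints): "Adverse event severity will be graded according to CTCAE, Version 4.03". The synopsis entry for the primary endpoints says the same.
- Synopsis, statistical analyses: "Adverse event severity will be graded according to NIH CTCAE Version 4.03".
- Section 10.6 applies the CTCAE v4.03 scale in Appendix 1 to AEs and to abnormal laboratory values, qualified by the words if appropriate.
- Section 10.7: "Any toxicities and/or abnormal laboratory findings should be investigated for aetiology and graded according to Appendix 1". Appendix 1 is CTCAE v4.03.

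Section 10.2.1 starts the same way. It requires severity on the CRF and adds "See Appendix 1 for details of the NCI CTCAEv4.03 toxicity grading scale". It then gives a three-grade table for pain and tenderness at injection sites (Table 7) and continues: "For all other reported adverse events, severity should be recorded and graded as". The table that follows has three levels: 1 mild, 2 moderate and 3 severe, the last meaning incapacitating. There is no Grade 4.

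Section 10.7 attaches actions to Grade 4: "Grade 4: Patients developing any Grade 4 toxicity should have treatment interrupted". It also withdraws a subject from treatment permanently for treatment-related Grade 4 toxicity.

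**The concern.** AE severity is part of the primary endpoint of a first-in-human study whose primary objective is safety. Section 10.2.1 is the instruction for data capture. If a site follows it literally, the CRF holds a functional mild/moderate/severe rating where the endpoint promises a CTCAE grade. Both scales use the numbers 1 to 3, so a recorded 3 does not show which scale produced it.

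This cannot simply be left to the SAP. A SAP can choose how to tabulate severity, but it cannot turn a three-level rating into a CTCAE grade without regrading each event.

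Two further effects are possible. The severity grades shown to the Safety Monitoring Committee may be compressed at the top, since an incapacitating event and a life-threatening one would both be recorded as 3. And the recorded grade may not match a Grade 4 interruption or withdrawal made under Section 10.7.

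**Working it through.** The protocol states no figure to reproduce. The check compares every place that sets or uses a severity scale.

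| Place | Scale | Top grade used in the text |
|---|---|---|
| Synopsis and 4.2.1, primary endpoint | CTCAE v4.03, unconditional | not stated |
| Synopsis, statistical analyses | CTCAE v4.03, unconditional | not stated |
| 10.2.1, first paragraph | refers to CTCAE v4.03 | not stated |
| 10.2.1, Table 7 (site pain/tenderness) | three-level | 3 |
| 10.2.1, all other AEs | generic three-level | 3 |
| 10.6 | CTCAE v4.03, if appropriate | not stated |
| 10.7 | CTCAE v4.03 via Appendix 1 | 4 |
| 13.6.4 | AEs categorised by severity, scale not named | not stated |

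**Does any text reconcile the scales?** None ranks them or maps one to the other. The phrase introducing the generic table comes directly after Table 7, so its natural meaning is every AE except injection-site pain and tenderness. Where the protocol does provide a fallback for items outside the grading scale, it says so: Section 10.6 has such laboratory abnormalities classed as clinically significant or not. That is a different rule from the Section 10.2.1 table.

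**Laboratory findings.** Section 10.5 says that "all laboratory data are collected and statistically analysed according to their respective toxicity gradings" and that abnormalities without symptoms should generally not be recorded as AEs. But Section 10.6 sends clinically significant results to the AE form, and Section 10.5 does the same for results that meet the SAE criteria. Such a finding would be graded by CTCAE in the laboratory analysis and, under Section 10.2.1, at no more than Grade 3 as an AE. One finding could then carry two grades.

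**Do the Grade 4 rules still work?** Yes. Section 10.7 requires grading by Appendix 1 within the dosing section. It also interrupts dosing, whatever the severity, for an event at least possibly related to treatment that the investigator judges to contraindicate further doses, and it stops dosing when changes pose a significant health risk.

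**Reach** (Section 5.1 for numbers; Section 12.3 for one dose in Part A and three in Part B):

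- Patients whose AE severity is recorded: 18 + 40 = 58.
- Planned administrations, active or placebo: 18 × 1 + 40 × 3 = 138.
- Administrations that a Grade 4 rule could still stop: none in Part A, which is single-dose; Part B doses 2 and 3 only, 40 × 2 = 80.

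These are upper bounds on exposure to the problem, not expected counts of misgraded events.

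**The case against.** The best case on the other side is that the intended scale is hardly in doubt. CTCAE is named in the endpoint, the synopsis, Sections 10.6 and 10.7, and the opening of Section 10.2.1 itself, so the generic table looks like left-over text. The consequences also look limited:

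- The dosing rules carry their own grading.
- Death, life-threatening events and hospitalisation are captured through the SAE criteria (10.3.1) and reported within 24 hours (10.3.3.1).
- The Safety Monitoring Committee sees individual patient data as well as aggregates (Section 11).
- The AE analysis focuses on subject incidence (13.6.4), and the study is descriptive (13.1).
- The generic table is worded for symptoms and fits an asymptomatic laboratory value poorly.
- Whether any grade is actually misrecorded depends on the CRF code list, which is not shown.

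Much of this stands. It rules out any claim that the stopping rules fail or that serious events would be hidden, and it makes 80 of 138 a ceiling that would be reached only if every Part B patient had a Grade 4 event before the second dose. It does not remove the conflict. The generic table is a positive instruction about what to record, it is not limited to terms outside CTCAE, and it is in the section an investigator consults when completing the form. Knowing which scale was intended does not recover a CTCAE grade that was never recorded.

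**Conclusion.** The concern holds. Section 10.2.1 contradicts the primary endpoint and Sections 10.6 and 10.7 on how AE severity is graded, and no text resolves it. Up to 58 patients could have severity recorded on a scale other than the one the endpoint names. A mismatch with the Grade 4 rules could bear on at most 80 of 138 administrations, all in Part B, and those rules can still be triggered through CTCAE grading.

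Confidence in the textual conflict is high. Its practical effect assumes that the CRF follows Section 10.2.1, which cannot be seen from the protocol; if the CRF already uses CTCAE grades, the harm is confined to confusing instructions. AE incidence, SAEs, withdrawals and vital signs are not affected. This should be fixed, but it is not a failure of subject protection.

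**What to change.** In Section 10.2.1, delete the three-level table for all other adverse events, or restrict it expressly to terms that CTCAE does not cover. Add one sentence stating that the CTCAE v4.03 grade, over its full range, is the recorded severity for every AE with a CTCAE term. Keep Table 7 only as an additional descriptor for injection-site pain and tenderness. Check that the CRF code list for severity matches.

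The actions in Section 10.7 need no change. The cost is one table removed or restricted, one sentence and one check of the code list, with no extra visits or assessments. If events have already been recorded on the three-level scale, they would need regrading individually from source.

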12.3 Withdrawal of subjects from study product

Investigational medicinal product is administered once during Part A of this protocol and three times during the conduct of Part B of this protocol.

Section 10.7 provides guidance for dose modification or discontinuation of IMP in the event of AEs or abnormal laboratory values.

If a subject permanently discontinues dosing with IMP, for example as a result of an AE, every attempt should be made to keep the subject in the study and continue to perform the required study related follow-up and procedures.

The ideal is to continue to follow the subject for the full study period or until resolution of the adverse event. If it is not possible for the subject to remain in the study for the full study period, every attempt should be made to keep the subject in the study up to the Exit Evaluation at Day 57. If the subject remains in the study but off study treatment, all study procedures should continue as per protocol.

If the subject will not remain in the study for all study related procedures, the Exit Evaluation should be performed wherever possible.

All subjects who discontinue study medication dosing should be followed for at least 30 days after the last dose of IMP in order to monitor subjects for possible post-treatment events which may occur after IMP has been discontinued.

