13.6.4 Adverse events

The primary analysis of adverse events will consider only treatment-emergent AEs (TEAEs), events occurring for the first time, or worsening, during or after the first administration of study drug. The analysis will focus on subject incidence, although for TEAEs of special interest, the number of events may also be provided. Tables summarizing TEAEs will be displayed by preferred term and system organ class (SOC). The analysis will also include the analysis of serious adverse events (SAEs) and the categorization of AEs by severity and relationship to study drug. The analysis of AEs leading to study withdrawal or deaths on-study will also be provided in tables and/or listings. Further details will be provided in the SAP.

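### In Protocol 10.2.1 the Definite causality category is easier to meet than Probable, and after the single Part A injection its abatement clause carries no dechallenge information

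*Protocol*

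**What the plan says.** Section 10.2.1 lists five categories (Unrelated, Unlikely, Possible, Probable, Definite) and directs that relationship be assessed with these definitions.

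- **Possible:** "The AE could have been produced by the subject's clinical state or study drug".
- **Probable:** reasonable timing, and the event "abates upon discontinuation of the study drug and cannot be reasonably explained by the known characteristics of the subject's clinical state".
- **Definite:** reasonable timing, and the event "abates upon discontinuation of the study drug and/or reappears when study drug is re-introduced". Nothing is said about other explanations.
- **Unrelated:** events clearly due to outside causes, with underlying disease given as an example.

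The same section adds that "These criteria in addition to good clinical judgment should be used as a guide for determining the causal assessment".

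On dosing, section 12.3 states: "Investigational medicinal product is administered once during Part A of this protocol and three times during the conduct of Part B of this protocol". On analysis, section 13.6.4 focuses on the incidence of treatment-emergent events and adds a "categorization of AEs by severity and relationship to study drug".

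**The concern.** A causality scale is useful only if each step up demands more evidence than the one below. Here the highest step demands less than the one beneath it. It omits the condition that does most to separate a drug reaction from the patient's own disease, and *and/or* allows a single piece of supporting evidence to suffice. That matters in a population where flares of rheumatoid arthritis (RA) are expected and are themselves followed as a safety outcome.

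The abatement clause is also written for continuing treatment. This product is given once in Part A and three times at weekly intervals in Part B, so for many events there is no ongoing treatment to stop. At stake are the meaning of the upper end of a planned safety table and the reliability of causality labels read one event at a time in a first-in-human study.

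**Working it through.** The protocol gives no figure to reproduce, so the check is logical.

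**Criteria, all from 10.2.1**
- T: timing is reasonable
- D: event abates on discontinuation
- N: not reasonably explained by the subject's clinical state
- R: event reappears on re-introduction

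**Rules as written**
- Probable = T and D and N
- Definite = T and (D or R), because *and/or* is satisfied by either

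**All combinations (2 × 2 × 2 × 2 = 16)**
- Probable: T, D and N fixed true, R free, giving 2.
- Definite: T true, 3 of the 4 (D, R) pairs, N free, giving 3 × 2 = 6.
- Probable but not Definite: 0, since D is true in every Probable case.
- Definite but not Probable: 6 − 2 = 4. In (T, D, N, R) order these are (1,1,0,1), (1,1,0,0), (1,0,1,1) and (1,0,0,1). In three of the four, N is false: the clinical state explains the event.

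**Part A (one dose, so R is always false; 8 combinations)**
- Probable: 1. Definite: 2.
- The extra Definite case is (1,1,0,0): a well-timed event that resolves and is explained by the clinical state. It also fits Possible and, if clearly due to RA, Unrelated.
- With R false, both upper categories require D. An event that persists therefore cannot be rated above Possible, whatever its cause.
- D is true of any self-limiting event, because nothing continues after the injection. A stricter reader could say that discontinuation never happens after one dose; then neither category is ever available in Part A. On neither reading does the clause test for a drug effect.

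**Part B (three weekly doses)**
- After doses 1 and 2 a later dose can be withheld or given, so dechallenge and rechallenge are possible.
- After dose 3 nothing remains to stop, and the limit on dechallenge is the same as in Part A.

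**Effect of nesting.** If Definite required T, D, N and R together, it would be met by 1 of 16 combinations, inside the 2 that meet Probable, and by 0 of 8 in Part A.

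These are counts of logical cases, not event rates. The protocol gives no proportion of events expected to resolve or to be judged well timed, so no misclassification rate can be derived from it.

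**The case against.** The strongest reply is that little depends on this boundary.

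- **Arm comparison.** A reader might infer that the relationship table cannot separate drug effects from transient background events. The protocol does not support that. Placebo is a randomised comparator for safety (section 5.1), assessing staff are blinded (8.2), and adverse events are summarised per treatment group (synopsis). A label that is too generous is equally so in both arms, so the contrast survives, though with few subjects: 12 active and 6 placebo in Part A, 30 and 10 in Part B.
- **Main summary.** Section 13.6.4 centres on incidence of treatment-emergent events regardless of causality; the relationship table is an addition. This stands.
- **Toxicity rules.** A reader might infer that dosing decisions are affected. The rules in 10.7 turn on whether an event is at least possibly related, or treatment related, and do not use the Probable/Definite line. This stands too.
- **Clinical judgement.** The criteria are a guide, and an investigator may place an RA-explained event under Unrelated or Possible. That softens the practical effect. But these are the protocol's only definitions, and a scale that must be overridden to come out in the right order needs rewording.
- **Part B.** Rechallenge is possible after doses 1 and 2, so the dosing mismatch is mainly a Part A matter (18 of 58 subjects) plus events after dose 3. The inversion itself applies to both parts.

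One qualification cuts the other way. Under section 11 the Safety Monitoring Committee sees only data blinded to allocation, so any causality labels it receives cannot be set against placebo. Whether it receives them, and what weight it gives them, would be in its charter, which is not at hand.

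**Conclusion.** The point holds as a defect in the definitions. As worded, every Probable event also meets Definite, and an event explained by the patient's RA can meet Definite while failing Probable: 6 qualifying combinations against 2 overall, and 2 against 1 in Part A. This rests only on reading *and/or* as either or both, and on the dosing counts in section 12.3.

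The consequence is limited. The Probable/Definite split in the relationship table is not interpretable, and single-event labels are unreliable, including any that reach the Safety Monitoring Committee. The primary safety comparison, treatment-emergent incidence by randomised arm, is not compromised. The correction is worth making because the error is plain and the cost is small.

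**What to change.** Reword the two definitions in 10.2.1 so that they are nested:

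- **Probable:** reasonable timing and no reasonable explanation by clinical state, other drugs or study procedures. Abatement on discontinuation counts only where the schedule makes it assessable.
- **Definite:** everything Probable requires, plus further evidence such as reappearance on a later dose.
- **Where the clauses apply:** limit discontinuation and re-introduction to Part B before the last dose, and state that they are not assessable in Part A.
- **Injection-site reactions:** do not let one qualify as Definite on its own, since saline is injected by the same route and at the same sites (section 5.2).

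The cost is protocol and case report form guidance wording; no dosing rule changes. The downside is that fewer events will be labelled Definite, and in Part A possibly none.
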